### **3.2 Exclusion Criteria**

Subjects meeting the following conditions are not eligible for participation in the study:

1. Subject has known radiographic evidence of metastatic disease, except for presence of positive lymph nodes from the surgical pathology. Pelvic/intraperitoneal lymph nodes less than 1.5 cm maybe considered nonspecific and the patient would be eligible (including those patients who were treated with radiation for oligometastatic disease). If there is any clinical suspicion for metastatic disease, CT and Bone Scan must be performed to rule out metastatic disease, within the last three months, per standard of care.
2. Subject has received any therapies that modulate testosterone levels (e.g., androgen ablative/anti-androgen therapy, 5 alpha reductase inhibitors) for a minimum of 12 months prior to study.
3. Subject has had prior or concomitant treatment with experimental drugs, high dose steroids, or any other cancer treatment within 4 weeks prior to the first dose of the study product.
4. Subject has consumed any Muscadine Plus over the past 2 months.
5. Subject has a known allergy to muscadine grapes, ellagic acid or rice.
6. Subject has uncontrolled concurrent illness including, but not limited to, ongoing or active infection, symptomatic congestive heart failure, unstable angina pectoris, cardiac arrhythmia, or psychiatric illness/social situations that would limit compliance with study requirements.
7. Subject has negative PSA doubling time (negative doubling time corresponds with decreasing PSA) Doubling time may be computed using the Sloan Kettering prediction tools posted at <http://www.mskcc.org/applications/nomograms/prostate/PsaDoublingTime.aspx>

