## 3. Eligibility Criteria

### 3.1 Inclusion Criteria

Patients meeting the following conditions are eligible for registration and participation in the study:

1. Subject has histologically or cytologically confirmed adenocarcinoma of the prostate
2. Subject has undergone definitive treatment (surgery, surgery with radiation therapy, cryotherapy, radiation therapy or brachytherapy) for the primary prostate tumor (prior chemotherapy is not allowed).

- a. A subject with a rising PSA post-prostatectomy should consider radiation as a potentially curative alternative. If subject declines radiation or is not a candidate for radiation, he may be considered eligible in this setting.
3. Subject has a rising PSA on a minimum of 3 time points (2 rises) within the 12 months prior to study initiation (this will include the PSA measurement taken at the screening visit, but not at the baseline day 0 study visit). The three time points must be at least 21 days apart. Note: Fluctuations in PSA are allowed per Bubley et al 1999 working group criteria. 
4. For purposes of calculating PSADT:
  - a) All PSA values used in the calculation should be  $\geq 0.10$  ng/ml and overall should follow a rising trend;
  - b) Record every available PSA drawn within the last 12 months;
  - c) The minimum requirement is 3 PSA values;
  - d) For radiotherapy only patients, record PSA nadir value and collection date.PSADT must be positive according to Memorial Sloan Kettering Cancer Center Prostate Cancer Nomograms under this link:  
<http://www.mskcc.org/applications/nomograms/prostate/PsaDoublingTime.aspx>
5. At least 2 PSA rises need to be after a normal Testosterone for those patients who had prior hormone therapy.
6. One of the following criteria must be met.
  - a. Absolute level of PSA  $>0.2$ ng/mL following surgery. (surgery only)
  - b. Absolute level of PSA  $>0.2$ ng/mL for subjects treated with multiple treatment modalities (e.g., surgery + radiation, surgery + cryotherapy, etc.).
  - c. A rise by 2 ng/mL or more above the nadir PSA will be considered the standard definition for biochemical failure after radiation therapy with or without hormonal therapy. (radiation only)
7. Subject is  $>18$  years of age.
8. Subject has life expectancy of greater than 12 months.
9. Subject has ECOG performance status 0, 1 or 2
10. Subject has testosterone level of  $\geq 150$  ng/dL at screening.
11. Subject has normal organ and marrow function as defined below:

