## **5. TREATMENT PLAN**

This is a randomized, double-blind, placebo controlled multicenter study to compare the change in slope and PSADT from baseline between placebo and MDX treatment groups. Approximately 500 subjects will be registered and genotyped to find 80 men with AA genotype for enrollment.

Those with AA genotype will be enrolled and randomized 1:1 (40 to placebo and 40 to MPX). Treatment on study will last 48 weeks and will be administered on an outpatient basis.

Appropriate dose delays and discontinuation recommendations for MPX are described in Section 6. Adverse event reporting requirements and potential risks are described in Section 7. No investigational or commercial agents or therapies other than those described below may be administered with the intent to treat the patient's malignancy.

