### **5.1 MPX Administration**

Each treatment cycle is 12 weeks (84 days). Patients will take 8 MPX pills or 8 placebo pills daily, for once daily oral dosing of 4000 mg MPX. Patients may continue to receive additional cycles of study drug and will be followed every 12 weeks with standard visits with their physician until completion of 48 weeks of study treatment, disease progression, or until they wish to discontinue the drug.

Patients will self-administer the assigned number of capsules on a daily schedule. Patients will return capsule containers and any unused study drug to the study coordinator or research nurse at each scheduled follow-up visits. Returns will be documented on the drug accountability log by the pharmacist or pharmacist designee.

Compliance with study product consumption will be evaluated by subject interview and by patient pill diaries (Appendix B) that will be collected at each visit. Compliance will be recorded as a percent of scheduled intakes of study product consumed. Non-compliance will be defined as consumption of <80% of the scheduled intakes of study product.

Patients will be asked to refrain from adding other vitamin or herbal supplements during the study period and follow-up. If a patient does not comply, he will first be counseled that he may be withdrawn from the study. If he persists in taking vitamins or herbal supplements, he will be withdrawn from the study.

Participants will be encouraged to administer the MPX capsules as follows:

- 1) MPX Capsules must be swallowed whole
- 2) MPX Capsules should be taken with water
- 3) MPX capsules should be taken at least 60 minutes prior to eating or 2 hours after eating
- 4) Ingestion of capsules may be spread out over 2 hours if necessary
- 5) Vomited doses will not be made up. If the vomiting occurs after 3 sequential doses and is thought to be related to study drug, the patient should refrain from taking additional MPX capsules and report this to study team.
- 6) If a dose is missed (forgotten at the usually administered time), it may be made up any time later that same day.

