### **5.3 General Concomitant Medication and Supportive Care Guidelines**

Patients may not be taking any other medications for the goal of treating their prostate cancer. If they are taking medications for other purposes, they may continue per the guidance of the doctor.

Patients who have an on-going study drug-related serious adverse event upon study completion or at discontinuation from the study will be contacted by the investigator or his/her designee periodically until the event is resolved or determined to be irreversible.

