### 11.1 Analysis Plans for Primary Objective

**PSA Slope:** Eligible patients must have a rising PSA with a minimum of 3 time points but up to 17 time points (2 rises at least 21 days apart) within the 12 months prior to study initiation (this could include the PSA measurement taken at the screening visit, but not at the baseline day 0 study visit). The pre-treatment slopes will be calculated based on these data prior to baseline (day 0). A minimum of three time points but up to five time points will be used for calculating on-study slopes: baseline, 12, 24, 36, and 48 week assessments. All data points will be used unless an assessment is unavailable, in which case the remaining time points will be used. There must be a minimum of three data points, and there will be no imputation of missing PSA values.

The primary objective will be based on the intent-to-treat (ITT) population and assessed with an ANCOVA model, with post-treatment PSA slope as the independent variable and study arm and baseline PSA slope as covariates. A two-sided t test at the 0.05 significance level will be used to determine if, adjusting for baseline, the post-treatment PSA slope has been reduced with MPX supplementation (Arm A). Scatterplots of post treatment PSA slope by baseline slope will be used to visualize the fitted ANCOVA model. Boxplots of the observed changes will also be used to visualize the results.

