### **11.4 Additional Analyses**

**Baseline Characteristic Analyses:** Qualitative baseline characteristics will be summarized with the number and percent of subjects in each treatment group with the characteristic. Quantitative characteristics (e.g., age, height, and weight) will be summarized with the median, mean, standard deviation, minimum value, and maximum value. Categorical characteristics will be tabulated.

The number and percent of subjects, who are randomized, treated with randomized study drug, prematurely discontinued study drug, are lost to follow up, and completed four 12 week cycles of follow-up after randomization will be summarized.

The number and percent of subjects with each medical history will be summarized. Fisher's exact test will be used to assess treatment group differences in the proportions of subjects with each medical history. The number and percent of subjects that receive each medication that is not the study drug will be summarized.

There will be no adjustment for multiple statistical comparisons. We recognize that carrying out multiple significant tests increases the risk of false positive results among the collection of all analyses. Therefore, except for the primary outcome, all other analyses are considered as secondary, tertiary, or exploratory.

**ECOG Performance Status:** ECOG Performance Status will be captured as on a 6-point categorical scale from 0 (normal activity) to 5 (dead) and summarized using shifts from baseline to the 24-week and 48-week evaluations. Baseline is defined as the last ECOG value prior to or on the date of randomization. The percentage of patients with an increase of at least 1 point from baseline will be presented for each treatment group at both the 24-week and 48-week evaluation time points.

**Adherence:** Participants who completed 4 cycles of study and had at least 80% of intake of the planned consumption will be defined as study compliant. An overall probability of study compliance will be estimated with a 95% confidence interval. The difference in proportion of compliance between two groups will be tested using Fisher's exact test at a two-sided alpha level of 0.05. Summary statistics will also be provided for the time from the first dose to the last dose of study drug.

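### Exclusion 2 states a minimum length of exposure where a 12-month look-back was almost certainly meant, and nothing bars starting the same drug classes for a non-cancer reason during the 48 blinded weeks

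*Combined protocol and SAP*

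**What the plan says.** **Entry.** Section 3.2, item 2, excludes a subject who has "received any therapies that modulate testosterone levels (e.g., androgen ablative/anti-androgen therapy, 5 alpha reductase inhibitors) for a minimum of 12 months prior" to study. The two items that follow use look-backs: item 3 covers the 4 weeks before first dose, and item 4 the past 2 months. Section 3.1, item 3, takes the qualifying PSA rises from values "within the 12 months prior to study initiation", and item 4 asks for every PSA in that period.

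**On study.** Two sentences limit other drugs, both by purpose. Section 5 reads "No investigational or commercial agents or therapies other than those described below may be administered with the intent to treat" the malignancy. Section 5.3 reads "Patients may not be taking any other medications for the goal of treating their prostate cancer", then adds "If they are taking medications for other purposes, they may continue per the guidance of the doctor". Neither mentions starting a drug for another purpose. Supplements are treated more strictly. Section 5.1 says "Patients will be asked to refrain from adding other vitamin or herbal supplements during the study period and follow-up", and a man who persists after counseling is withdrawn.

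**Analysis.** Section 11.1 fits the on-study slope to the PSAs at baseline and weeks 12, 24, 36 and 48: "All data points will be used unless an assessment is unavailable". Concomitant medications are recorded at visits (section 10) and described: "The number and percent of subjects that receive each medication that is not the study drug will be summarized" (section 11.4). No rule deals with a drug that alters PSA.

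**The concern.** Read literally, exclusion 2 works against its evident purpose. Thirteen months on a 5-alpha-reductase inhibitor excludes a man, but six months ending at screening does not. Such a man's pre-treatment slope would be distorted, and that slope is the ANCOVA covariate. His pre-treatment doubling time, a stratification factor, would be distorted too. With 16 to 17 sites planned (section 11, sample size and accrual), the sentence could be read in more than one way.

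The on-study gap touches the primary outcome directly. A PSA-lowering drug started in the blinded period reduces a man's fitted log slope whichever capsule he takes. The plan treats these classes as disqualifying at entry and restricts added vitamins on study, yet it leaves new starts of the same classes uncontrolled when the reason is not cancer.

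**Working it through.** **The wording.** Three points support a look-back as the intent of exclusion 2: the look-backs in items 3 and 4, the match with the 12-month PSA window in section 3.1, and the oddity of a rule that admits recent users while excluding long-term ones. On that reading, entrants have been off these drugs throughout the pre-treatment window, and only the wording needs correcting.

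Other criteria narrow the literal gap without closing it. Section 3.1, item 5, requires two PSA rises after a normal testosterone in men with prior hormone therapy. Item 10 requires testosterone of at least 150 ng/dL at screening. Exclusion 3 covers cancer treatment in the last 4 weeks. These limit recent androgen ablation, but none by its terms catches a 5-alpha-reductase inhibitor taken for a benign reason.

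**The plan's power.** Inputs from section 11: 39 per arm, difference 0.05, SD of post-treatment slope 0.075 (Table 1), two-sided 5%.

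- Standard error of the difference = 0.075 × √(2/39) = 0.0170.
- Noncentrality = 0.05 / 0.0170 = 2.94.
- Noncentral t with 75 degrees of freedom, correlation 0, no interim look: power 82.8% (normal approximation 83.7%). The stated 83% reproduces.

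**One man's slope.** Assumption, not in the documents: the drug causes one lasting PSA fall of 50% (range 30% to 60%), and all five PSAs are available. Visit times in months are 0, 2.76, 5.52, 8.28 and 11.04. Centered, they are -5.52, -2.76, 0, 2.76 and 5.52, with sum of squares 76.16. The slope shift is ln(1 - fall) × (sum of centered times from the first affected visit onward) / 76.16. That sum is 5.52 for week 12 or 48 and 8.28 for week 24 or 36. For a 50% fall, ln(0.5) = -0.693, so the shift is -0.693 × 5.52 / 76.16 = -0.0502, or -0.693 × 8.28 / 76.16 = -0.0753.

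| PSA fall | First seen week 12 or 48 | First seen week 24 or 36 |
|---|---|---|
| 30% | -0.0258 | -0.0388 |
| 50% | -0.0502 | -0.0753 |
| 60% | -0.0664 | -0.0996 |

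At a 50% fall, one such man moves his arm's mean by 0.0502/39 = 0.0013 to 0.0753/39 = 0.0019, which is 0.08 to 0.11 of the standard error.

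**The whole trial, starts balanced across arms.** Let a share f of men start such a drug, with the first affected visit equally likely among the four. The difference stays at 0.05 and the SD becomes √(0.075² + f × mean(s²) - (f × mean(s))²), where s is the shift. At a 50% fall, mean(s) = -0.0628 and mean(s²) = 0.00410.

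| PSA fall | f = 5%: SD, power | f = 10%: SD, power |
|---|---|---|
| 30% | 0.0753, 82.5% | 0.0757, 82.1% |
| 50% | 0.0763, 81.5% | 0.0774, 80.4% |
| 60% | 0.0772, 80.6% | 0.0792, 78.6% |

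One man in 78 at a 50% fall gives an SD of 0.07535 and power of 82.5%.

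**A chance imbalance.** If two placebo men and no MPX men start, the expected difference shrinks by 2 × 0.0628/39 = 0.0032. Half the added variance goes into the pooled SD, because only one arm is affected. Power is then about 77% at a 50% fall (80% at 30%, 74% at 60%). This is a deliberately unfavorable split.

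**The case against.** The strongest case is that this is a copy-edit joined to a hypothetical. The literal reading of exclusion 2 makes so little sense that sites are unlikely to apply it. Section 4.1 has eligibility confirmed centrally, section 2.3 speaks of a recovered testosterone, footnote 6 of the study calendar records dates of prior hormonal therapy, and a man whose PSA fell on a new drug could fail the rising-PSA requirement. On study, cancer-directed hormone therapy is already barred, every man has had definitive treatment of the prostate, and any new drug would appear in the concomitant medication record. Both the size of the PSA fall and the share of men affected come from outside the documents. The central power loss is small beside the simulation error in Table 1, about 0.85 point with 2000 runs. The supplement rule is also a weak comparator, because supplements overlap with the antioxidant intervention itself.

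Much of this stands. It limits the size of the problem, and it rules out any claim of systematic bias. Placebo-only starts are a chosen worst case and do not justify a higher grade. It does not remove the point, however. An operative eligibility rule says something other than what it means, and central confirmation applies the same sentence. Recording a new drug makes it visible but does not discourage it.

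**Conclusion.** The concern holds and is minor. Exclusion 2 is worded as a minimum duration. That a 12-month look-back was intended is an inference, though a well-supported one. No sentence bars starting a 5-alpha-reductase inhibitor, or another testosterone-modulating drug, for a non-cancer reason in the 48 blinded weeks.

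For an affected man the distortion can equal or exceed the full design difference. For the trial, the central loss is about 1 to 2.5 points of power, given a 50% PSA fall, 5% to 10% of men affected and balance between arms. If only one man is affected, or none, it is negligible. The effect is added noise and possible chance imbalance. The plan's stated power is not in dispute.

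**What to change.** 1. In section 3.2, item 2, replace the time phrase so that receipt of any of the named therapies *within the 12 months before study entry* excludes.
2. Add to section 5.3: *The drug classes named in exclusion 2 may not be started for non-cancer reasons during the 48 blinded weeks unless medically necessary. If one is started, record its start and stop dates and continue to collect PSAs.*

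The primary intention-to-treat ANCOVA stays as written, and no randomized man is removed. The cost is one line in 3.2 and two sentences in 5.3, since concomitant medications are already recorded at visits. A few men whom the literal wording would have admitted become ineligible. The sample size, the test and the stated power are unchanged.

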### **3.3 Inclusion of Minorities**

Men of all races and ethnic groups are eligible for this trial.

## **4. SUBJECT REGISTRATION AND DATA REPORTING**

### **4.1 Subject Registration**

After pre-screening, eligible patients with qualified AA genotype of *SOD2* gene will be registered on study centrally at the Sidney Kimmel Comprehensive Cancer Center (SKCCC) by the Coordinating Center Study Manager.

To register a patient, the following documents must be completed and emailed to SKCCC Study Manager:

- Signed patient consent form
- Research authorization/HIPAA form
- MAP Trial Registration Request Form
- Copies of the following records required for assessment of eligibility:
  - Prostate cancer pathology report
  - Baseline laboratory studies including CBC with differential, liver and kidney function tests, testosterone, and PSA values
  - Other materials considered pertinent for confirming patient eligibility

Upon receipt of complete packet, the Study Manager will confirm eligibility within 48 hours. Issues that would cause treatment delays should be discussed with the Protocol Chair and SKCCC Study Manager.

Each participating institution will receive MPX/placebo investigational products (IP) through a designated distribution facility contracted by the study after confirmed site activation. Shipping and order details are included in the study operations manual.

### **Randomization**

Once eligibility is confirmed, patients will be randomized to a treatment group according to the randomization schedule. Patients will be randomized to receive either placebo or MPX in a 1:1 ratio.

The investigators, study site personnel except designated pharmacy staff, and the subject will remain blinded to each subject's treatment throughout the course of the study.

### **Stratification**

Stratification will be by pretreatment PSADT ( $\leq 9$  or  $>9$  months) and Grade Groups (Grade Groups 1 and 2, equivalent to Gleason  $\leq 3 +4$ , and Grade Groups 3, 4 and 5, equivalent to Gleason  $\geq 4 +3$ ).

## **4.2 Data Reporting and Regulatory Requirements**

All information will be collected on study-specific CRFs by study staff. These data will be reviewed for completeness and accuracy by the Principal Investigator at each site and remote-monitored by SKCCC Study Manager or Monitors.

### The Protocol Chair

The Protocol Chair, [name], is responsible for performing the following tasks:

- Coordinating, developing, submitting, and obtaining approval for the protocol as well as its subsequent amendments
- Assuring that all participating institutions are using the correct version of the protocol
- Taking responsibility for the overall conduct of the study at all participating institutions and for monitoring the progress of the study
- Reviewing and ensuring reporting of Serious Adverse Events (SAEs)
- Reviewing data from all sites

### Lead Center

The Lead Center (SKCCC) is responsible for performing the following tasks:

- Ensuring that IRB approval has been obtained at each participating site prior to the first patient registration at that site, and maintaining copies of IRB approvals from each site.
- Managing central patient registration
- Collecting and compiling data from each site
- Establishing procedures for documentation, reporting and submitting of AE's and SAE's to the Protocol Chair and all other applicable parties.
- Facilitating audits by securing selected source documents and research records from participating sites for audit, or by auditing at participating sites.

### Participating Sites

Participating sites are responsible for performing the following tasks:

- Following the protocol as written, and the guidelines of Good Clinical Practice (GCP).
- Submitting data to the Lead Center (SKCCC)
- Registering all patients with the Lead Center (SKCCC) by submitting registration form, signed informed consent, and eligibility documentation promptly
- Providing sufficient experienced clinical and administrative staff and adequate facilities and equipment to conduct a collaborative trial according to the protocol
- Maintaining regulatory binders on site and providing copies of all required documents to the Lead Center (SKCCC)
- Collecting and submitting data according to the schedule specified by the protocol

